6.2.1. Statistical methods: analysis of correlated Data Using Generalized Estimating Equations

Average proportion of sputum samples positive for bacteria/viruses and its 95% CI will be computed using a GEE model. GEE approach uses weighted combinations of observations to extract the appropriate amount of information from correlated data such as the response measurements across multiple stable visits on the same patient (Burton, 1998).

For the purpose of the analyses a binomial distribution for the response variable (presence or absence of bacterial/viral pathogens in the sputum) with logit as link function will be assumed and an exchangeable correlation matrix will be chosen to account for the within-patient correlations.

The exchangeable correlation matrix assumes that the correlation between any two responses of the i^{th} individual is the same.

CONFIDENTIAL

201112 (EPI-NTHI-001 BOD APA)
 Statistical Analysis Plan Amendment 2 Final

Other commonly used within-patient correlation matrices are as follows:

- Independence, repeated observations are uncorrelated
- Unspecified (unstructured), correlations within any two responses are unknown and need to be estimated
- Autoregressive of first order [AR(1)], assuming the interval length is the same between any two observations. Measurements taken further apart are less correlated than those taken closer together.

The model with the exchangeable correlation matrix will be adopted in the main analysis. Models with the other matrices could be run as sensitivity analyses. QIC and the related QICu statistic will be used to compare GEE models with different correlation matrices.

SAS codes

```
ods output ParameterEstimates=out_parm ClassLevels=Class;
proc genmod data=<dataset> descending;
  class pid;
  model y = / dist = bin link = logit lrci ;
  Repeated subject=pid/sorted corr=cs PRINTMLE;
  by bacteria visit;
run;

data result;
  set out_parm(where=(parameter='Intercept') drop=ChiSq ProbChiSq DF);
  format percent LL UL percent8.1;
  Percent=exp(estimate) / (1+exp(estimate));
  LL=exp(LowerLRCL) / (1+exp(LowerLRCL));
  UL=exp(UpperLRCL) / (1+exp(UpperLRCL));
  unit=_N_;
run;
```

where pid = personal identifier, y = positivity to pathogen (0, 1), bacteria = type of bacteria, visit = type of visit (stable or exacerbation).

The REPEATED statement invokes the GEE method, specifies the correlation structure, and controls the displayed output from the GEE model. The option SUBJECT = PID identifies *pid* as the clustering variable, and the CORR = CS option specifies an exchangeable working correlation structure. Other matrices will be specified as CORR =: IND [independence], UN [unstructured], AR(1) [autoregressive (1)].

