6.2. Analysis of primary objective

The analysis of the primary objective will be performed on the FAS.

Average proportion of patients with sputum samples positive for bacterial or viral pathogens overall and for specific species, and its exact 95% confidence interval (CIs) will be computed at any stable scheduled visit and at any exacerbation visit for the entire study period. In addition, the average proportion of sputum samples positive for bacterial and viral pathogens overall and for specific species, and its 95% confidence interval will also be computed at any stable scheduled visit and at any exacerbation visit for the entire study period. Confidence intervals will be estimated using a Generalized Estimating Equations (GEE) model assuming a binomial distribution for the response variable with logit as link function and a compound symmetry correlation matrix (exchangeable structure) to account for the within-patient correlations (Liang, 1986) (more details in section 6.2.1). If the GEE model will not run due to only one level of the outcome variable, the exact 95% confidence interval will be computed. Proportion of patients with sputum samples positive for bacterial/viral pathogens overall and for specific species, will be computed, with exact 95% CIs, at each stable* scheduled visit (visit 1, visit 2, visit3) and at each exacerbation visit confirming acute exacerbation**.***.

* A confirmed stable visit will be defined as a scheduled study visit for which the investigator confirms in the eCRF that the patient is stable/has recovered from a previous exacerbation.

** If an AECOPD occurs at the time when one of the scheduled [stable] study visits is planned, it should be handled and recorded as an AECOPD visit. If possible, the stable study visit should be re-scheduled to a later date, within the ± 14 days' time window from the scheduled appointment, when the patient is stable again.

*** The definition of acute exacerbation of COPD (AECOPD) event is detailed in section 12.

CONFIDENTIAL

201112 (EPI-NTHI-001 BOD APA)
 Statistical Analysis Plan Amendment 2 Final

In details the following pathogens will be evaluated:

- Bacteria including, but not necessarily limited to, *H. influenzae**, *M. catarrhalis*, *S. pneumoniae*, *S. aureus*, *P. aeruginosa*, *K. pneumoniae* and *A. baumannii* by bacteriological methods (culture).

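### SAP 6.2.1: the printed SAS program reports independent-binomial likelihood-ratio limits for the proportion of positive sputum samples, not the GEE limits the text promises

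*SAP*

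**What the plan says.** SAP 6.2 reports two kinds of proportion for the primary objective. One is at patient level, with exact CIs. The other is at sample level: "In addition, the average proportion of sputum samples positive for bacterial and viral pathogens overall and for specific species, and its 95% confidence interval" are computed over all stable visits and over all exacerbation visits. For the sample-level result the model is a GEE with binomial response, logit link and "a compound symmetry correlation matrix (exchangeable structure) to account for the within-patient correlations". Section 6.2.1 repeats the commitment: "Average proportion of sputum samples positive for bacteria/viruses and its 95% CI will be computed using a GEE model".

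Section 6.2.1 then prints the program. Its key lines are:

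- the table captured: "ods output ParameterEstimates=out_parm ClassLevels=Class"
- the model: "model y = / dist = bin link = logit lrci"
- the clustering: "Repeated subject=pid/sorted corr=cs PRINTMLE"
- the lower limit: "LL=exp(LowerLRCL) / (1+exp(LowerLRCL", with `UpperLRCL` treated the same way for the upper limit

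The reported percentage is the inverse logit of the estimate in the same captured table. On alternative correlation structures the section adds: "Other matrices will be specified as CORR =: IND [independence], UN [unstructured], AR(1) [autoregressive (1".

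**The concern.** The text promises one interval and the program delivers another. The `REPEATED` statement does fit a GEE, but nothing from that fit reaches the results data set. The program would run without error and give plausible limits, which would then be labelled as adjusted for within-patient correlation. Changing the `CORR=` option would alter none of the exported numbers.

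The primary objective is estimation, and these sample-level intervals are part of its result. Where samples from one patient resemble each other, intervals that ignore this are too narrow. The SAP's own reason for choosing a GEE is to allow for that resemblance.

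**Working it through.** **1. Which fit the limits come from.** `LRCI` requests likelihood-ratio limits, and `LowerLRCL` and `UpperLRCL` are the columns that hold them. Such limits solve 2[ℓ(p̂) − ℓ(p)] = 3.84 for a log-likelihood ℓ. A GEE is defined by estimating equations and has no ℓ. The only likelihood available is that of the ordinary binomial model with an intercept, ℓ(p) = x log p + (n − x) log(1 − p), in which all n samples are independent. `PRINTMLE` and the `ParameterEstimates` table point the same way. No other section of the SAP corrects this.

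**2. The plan's own interval figures.** No figure in the plan was produced by this program. The nearest is Protocol Table 12, which assumes independent samples. For 30% of N = 140 (42 positive), the Clopper-Pearson limits give 22.6–38.3%, as printed. All 24 entries of the table reproduce.

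**3. Inputs for the size of the effect.**

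- Stable samples: three scheduled visits (SAP 2).
- Patients: 80% of 200 = 160 (Protocol 9.2, completion assumption).
- Prevalence: 20% and 5%, both rows of Table 12.
- ICC: not given in the documents, so 0 to 0.5 is assumed.

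**4. Worked example, 96/480 positive.**

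- As coded: 2[96 log(0.2/p) + 384 log(0.8/(1 − p))] = 3.84 gives 16.6–23.7%, whatever the ICC.
- Adjusted for ICC 0.3 with three samples per patient: variance inflation is 1 + 2 × 0.3 = 1.6. On the logit scale SE = √(1.6 / (480 × 0.2 × 0.8)) = √(1.6/76.8) = 0.144. The limits are −1.386 ± 1.96 × 0.144, which back-transform to 15.9–24.9%.
- A GEE with sandwich SE, run on a constructed data set with estimated ICC 0.30, gives the same 15.9–24.9%.

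**5. Coverage and width.** The GEE limits are wider by about √(1 + 2·ICC). Approximate coverage of the coded limits is 2Φ(1.96/√(1 + 2·ICC)) − 1. The simulation used beta-binomial data, 160 × 3 samples, 20% positive and 4000 replicates per setting:

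| ICC | √(1+2·ICC) | Coverage as coded, formula | Coverage as coded, simulated | Mean width as coded (points) | Mean width GEE (points) |
|---|---|---|---|---|---|
| 0 | 1.00 | 95% | 95% | 7.1 | 7.1 |
| 0.05 | 1.05 | 94% | 94% | 7.1 | 7.5 |
| 0.1 | 1.10 | 93% | 92% | 7.1 | 7.8 |
| 0.2 | 1.18 | 90% | 89–90% | 7.1 | 8.4 |
| 0.3 | 1.26 | 88% | 87% | 7.1 | 9.0 |
| 0.5 | 1.41 | 83% | 83% | 7.1 | 10.1 |

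The GEE limits cover about 95% throughout. At 5% prevalence, coverage as coded falls from 94% (ICC 0) to about 86% (0.3) and 81% (0.5).

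**6. Exacerbation samples.** The assumed mean is 1 visit × 80% evaluable = 0.8 per patient (Protocol 9.2), with overdispersion 1 to 2 as in Protocol Table 13. Coverage as coded is 95% at ICC 0, 92–93% at 0.1, 88–92% at 0.3 and 84–90% at 0.5. At ICC 0.3 the GEE limits are 1.08 to 1.16 times as wide.

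**7. Check with other inputs.** This used 180 patients with one to three stable samples each (mean 489 in total), 30% positive and 600 runs. At ICC 0.2, 0.4 and 0.6, coverage was 90.5%, 85.2% and 82.5% as coded, against 95.0%, 94.3% and 94.7% for the GEE. The reported percentage is also the crude proportion. Its mean absolute gap from the GEE estimate was 0.1–0.4 points for stable samples and 0.7–1.7 points for exacerbation samples.

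**The case against.** The strongest reply is that the prose governs and is right, and that the SAP's code blocks are templates. They contain dataset placeholders, the Cox code in 6.3.5.2.1 calls one of its features an example, and it lists sex as a class variable but leaves it out of the model. A careful programmer might therefore follow the prose. That makes the harm conditional on the code being used as printed. But 6.2.1 does not call its own program an example; it defines the program's variables and explains its options. A SAP whose text and code disagree on a primary-objective interval needs correcting either way.

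Other points stand in part:

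- **Alternative matrices.** The SAP says these could be run, so they are optional, and it compares them by QIC and QICu rather than by interval width. In balanced data, correct GEE sandwich limits are also the same under independence and exchangeable structures. Unchanged limits would therefore not by themselves reveal the error.
- **ICC.** Its size is assumed. At about 0.05 the shortfall is small.
- **Complete stable samples.** Three per patient is the upper end. With 80% yield at stable visits (an assumption borrowed from the exacerbation figure), coverage as coded is about 90% at ICC 0.3 and 85% at 0.5.
- **Small subsets.** With 45 patients, 5% prevalence and ICC up to 0.3, the coded limits covered 94–97%, so undercoverage is not universal.
- **Consequence.** SAP 7 makes all analyses descriptive, and the patient-level and per-visit proportions use exact CIs.

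**Conclusion.** The concern holds. As printed, the 6.2.1 program does not produce the interval that 6.2 and 6.2.1 specify, and its point estimate is likewise the crude proportion. For stable samples under the main assumptions (160 patients, three samples each, 20% positive), a nominal 95% interval covers about 92% at ICC 0.1 and 83% at 0.5. The loss is smaller for exacerbation samples and when fewer stable samples are obtained. That the limits ignore clustering follows from the code alone; how much this matters depends on an ICC the documents do not give. No test or decision rule is affected. It should be corrected because the error falls on a reported primary-objective result and would not be visible in the output.

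**What to change.** In the SAP 6.2.1 program:

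- Capture the GEE estimates with empirical (sandwich) standard errors, ODS table `GEEEmpPEst` in PROC GENMOD, instead of `ParameterEstimates`. The table name is software knowledge rather than document content.
- Back-transform that table's estimate and confidence limits for the percentage, LL and UL, and adapt the intercept filter and the drop list to its column names.
- Delete `LRCI` and `PRINTMLE`.
- Keep the existing exact-CI fallback for outcomes with only one level.

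SAP 6.4.4 promises the same type of GEE interval for apparition and acquisition and prints no code. If the 6.2.1 program is reused there, use the corrected version.

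The cost is a few lines of code and no new data. The sample-level intervals will be wider wherever samples correlate within patients, and the percentages may shift slightly where patients contribute unequal numbers of samples.

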6.3. Analysis of secondary objectives

The analyses of the secondary objectives will be performed on the full analysis set.

CONFIDENTIAL

201112 (EPI-NTHI-001 BOD APA)
 Statistical Analysis Plan Amendment 2 Final

6.3.1. Concordance between molecular (PCR) and bacteriological methods

The frequency distribution of sputum samples positive or negative for specific bacterial species (including but not necessarily limited to *H. influenzae*, *M. catarrhalis*, *S. pneumoniae*, *S. aureus* and *P. aeruginosa*) obtained from PCR will be tabulated versus results obtained from culture at any visit (stable scheduled visits or AECOPD visits).

The concordance between culture and PCR, at any visit, will be evaluated using the Cohen's kappa (κ) statistic and 95% CI. Concordance will be interpreted as good (>0.79), substantial (0.60–0.79), moderate (0.40–0.59), fair (0.21–0.39) or no concordance (<0.21) (McHugh, 2012).

Proportion of patients with sputum samples positive for bacterial pathogens (including but not necessarily limited to *H. influenzae*, *M. catarrhalis*, *S. pneumoniae*, *S. aureus*, *P. aeruginosa*, *K. pneumoniae* and *A. baumannii*) by PCR will be computed, with 95% CIs, at each and any stable scheduled visit and at each and any AECOPD visit confirming acute exacerbation.

6.3.2. Proportion of potential bacterial/viral pathogens by country, GOLD grade and by AECOPD severity

Average proportion of patients with sputum samples positive for bacterial or viral pathogens overall and for specific species, will be computed, with 95% CIs, at any stable scheduled visit and at any AECOPD visit confirming acute exacerbation [mild, moderate, severe] by GOLD classification [GOLD 2, 3, 4].

Average proportion of patients with sputum samples positive for bacterial or viral pathogens overall and for specific species, will be computed, with 95% CIs, at any stable scheduled visit and at any AECOPD visit confirming acute exacerbation by country.

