4.1. Number of subjects/ centres

The target is to enrol approximately 200 eligible moderate to very severe COPD patients. Refer to Section 9.2 for a detailed description of the criteria used to estimate the sample size.

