9.2. Determination of sample size

The primary objective of this study is to describe the proportion of bacterial and viral pathogens (overall and by species) detected in sputum in stable COPD and during AECOPD.

Assuming around 90% of the All Enrolled Set participated in the study, on average 1 AECOPD visit and 80% of the above population set can provide an evaluable sputum sample at AECOPD, for 240, 200, 160, and 50 enrolled subjects, one may expect around 180, 140, 120, 40 sputum samples, respectively. Assuming that results from these sputum samples are independent and that the between country variability is much smaller than the within country variability, we would have the following 95% exact confidence interval for different incidences in sputum samples from exacerbations (see [Table 12](#)).

Table 12 Exact 95% confidence intervals of the percentage of occurrence of a specific bacterium from sputum collected during AECOPD

%	Number of evaluable sputum samples during AECOPD			
	N=180	N=140	N=120	N=40
5	[2.3 ; 9.3]	[2.0 ; 10.0]	[1.9 ; 10.6]	[0.6 ; 16.9]
10	[6.0 ; 15.3]	[5.6 ; 16.2]	[5.3 ; 16.8]	[2.8 ; 23.7]
20	[14.4 ; 26.6]	[13.7 ; 27.6]	[13.3 ; 28.3]	[9.1 ; 35.6]
30	[23.4 ; 37.3]	[22.6 ; 38.3]	[22.0 ; 39.0]	[16.6 ; 46.5]
40	[32.8 ; 47.6]	[31.8 ; 48.6]	[31.2 ; 49.3]	[24.9 ; 56.7]
50	[42.5 ; 57.5]	[41.4 ; 58.6]	[40.7 ; 59.3]	[33.8 ; 66.2]

N = total number of evaluable sputum samples during AECOPD.

One of the secondary objectives is to estimate the incidence rate of all-cause AECOPDs in the study population.

Assuming around 80% of the all enrolled set completed the study, for 240, 200, 160 and 50 subjects enrolled, one would have at least 190, 160, 130 and 40 subjects evaluable respectively. Assuming further that around 80% of the subjects can provide an evaluable sputum sample at AECOPD, this would lead to around 150, 130, 100, 30 subjects (see [Table 13](#)).

Table 13 95% confidence intervals of AECOPD incidence rates with different overdispersion values

			$\Phi = 1$		$\Phi = 1.5$		$\Phi = 2$	
0.2 AECOPD/ subject/ year			95% CI*		95% CI*		95% CI*	
T	n	Value (n/T)	LL	UL	LL	UL	LL	UL
30	6	0.20	0.04	0.36	0.00	0.40	-0.03	0.43
100	20	0.20	0.11	0.29	0.09	0.31	0.08	0.32
130	26	0.20	0.12	0.28	0.11	0.29	0.09	0.31
150	30	0.20	0.13	0.27	0.11	0.29	0.10	0.30
1 AECOPD/ subject/ year			95% CI*		95% CI*		95% CI*	
T	n	Value (n/T)	LL	UL	LL	UL	LL	UL
40	40	1.00	0.69	1.31	0.62	1.38	0.56	1.44
130	130	1.00	0.83	1.17	0.79	1.21	0.76	1.24

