11.5. Methodology for computing CI

- All CI computed will be two-sided at 95% significant level.
- The exact 95% CIs for a proportion within a group will be calculated using Clopper Pearson method [[Clopper 1934](#)].

12. ANNEX 2: AECOPD DEFINITION AND CALCULATION RULE**12.1. Definition, onset, recovery, duration of an AECOPD event**

AECOPD events are confirmed according to investigator judgment after an AECOPD visit which is aimed to exclude worsening in symptoms not related to an AECOPD event.

AECOPD visits are scheduled after an electronic Diary Card alert confirmed by the investigator (by phone call or at the study site) or after spontaneous site visits due to worsening symptoms without any alert.

Electronic Diary Card alerts refer to daily symptoms recorded the morning after (also called morning symptoms). Alerts are based on the Anthonisen criteria:

- Worsening of two or more of the following major symptoms for at least two consecutive days*^{***}: dyspnea, sputum volume, sputum purulence (colour)

Or

- Worsening of any major symptom together with any of the following minor symptoms for at least two consecutive days*^{***}: sore throat, colds (nasal discharge and/or nasal congestion), fever (oral temperature $\geq 37.5^{\circ}\text{C}$) without other cause, increased cough, increased wheeze.

** The same two symptoms do not have to be present on both days as long as at least one major symptom is present on both days.*

CONFIDENTIAL

201112 (EPI-NTHI-001 BOD APA)
 Statistical Analysis Plan Amendment 2 Final

AECOPD onset will be defined as the first day of the two consecutive days of worsening symptoms.

AECOPD recovery will be determined/confirmed by the investigator/delegate during (a) follow-up phone call(s) which will take place every 2 weeks until the AECOPD has resolved. The end date will be based on when the investigator/delegate determines that the AECOPD symptoms have resolved. In determining this end date, consideration will be given to symptoms recorded in the electronic Diary Card and patient assessment during the phone calls.

AECOPD duration will be defined as the number of days from AECOPD onset (included) and AECOPD recovery (not included).

Duration = date2 – date1 + 1,

with date2: AECOPD recovery date,

date1: AECOPD onset date

12.2. Recovery and duration of an exacerbation according to EXACT-PRO:

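### The 95% CI for the culture–PCR kappa makes no provision for repeated samples per patient; the default interval will be too narrow if disagreement is correlated within patient

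*SAP*

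**What the plan says.** Concordance between PCR and culture is the first secondary objective listed in both documents. Under SAP 6.3.1, sputum samples positive or negative by PCR for each species are "tabulated versus results obtained from culture at any visit (stable scheduled visits or AECOPD visits"). The section continues: "The concordance between culture and PCR, at any visit, will be evaluated using the" Cohen's kappa, with this instruction on the interval and its reading: "statistic and 95% CI. Concordance will be interpreted as good (>0.79"), followed by substantial (0.60–0.79), moderate (0.40–0.59), fair (0.21–0.39) and none (below 0.21).

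The general section on intervals, SAP 11.5, adds two rules: "All CI computed will be two-sided at 95% significant level" and "The exact 95% CIs for a proportion within a group will be calculated using Clopper Pearson method". Neither gives a variance for kappa or deals with several samples from one patient. Protocol 9.6 gives no method for a kappa interval.

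Elsewhere the SAP does deal with repeated data. For the pooled positivity proportions (SAP 6.2.1), "an exchangeable correlation matrix will be chosen to account for the within-patient correlations". SAP 6.4.4 uses GEE for acquisition and apparition and patient-stratified conditional logistic models for the odds ratios. The recurrent-event Cox code in SAP 6.3.5.2.1 uses a covariance aggregated by patient.

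**The concern.** Each patient can give three stable samples and one more at each AECOPD visit. The usual large-sample standard error of kappa treats every culture–PCR pair as independent. A programmer following SAP 6.3.1 and 11.5 has no instruction to do anything else.

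If a patient whose culture misses a PCR-positive species tends to do so again, the pairs carry less information than their number suggests, and the interval is too short. The protocol offers one plausible source. Section 1.2 says culture results can differ between laboratories because testing methods differ, and section 6.5.3 places culture at the investigator's institution and/or a designated laboratory. Samples from one patient that go to the same laboratory would share its yield.

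At stake is how firmly a species appears to sit in one of the SAP's verbal bands, most of which are about 0.2 wide.

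**Working it through.** **1. The plan's own figure.** The documents give no sample size or precision for kappa. The nearest figure is the AECOPD sample count in Protocol 9.2. The inputs are 200 patients ("The target is to enrol approximately 200 eligible moderate to very severe COPD patients"), 90% participation ("Assuming around 90% of the All Enrolled Set participated in the study"), one AECOPD visit on average and 80% evaluable: 200 × 0.90 × 0.80 = 144, against around 140 stated. The exact intervals of Table 12 also reproduce to one decimal.

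**2. Samples per patient.**
- Participating patients: 200 × 0.90 = 180.
- Stable samples: 180 × 3 × 0.90 = 486. The 90% sampling rate is an assumption.
- AECOPD samples: 144.
- Total: 486 + 144 = 630, and 630 / 180 = 3.5 per patient.

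**3. Agreement scenario (assumed).** PCR is positive in 35% of samples. Culture is positive in 55% of PCR-positive and 4% of PCR-negative samples.
- Observed agreement: 0.35 × 0.55 + 0.65 × 0.96 = 0.8165.
- Culture-positive share: 0.35 × 0.55 + 0.65 × 0.04 = 0.2185.
- Chance agreement: 0.35 × 0.2185 + 0.65 × 0.7815 = 0.5845.
- Kappa = (0.8165 − 0.5845) / (1 − 0.5845) = 0.558.

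**4. Simulation.** There were 3000 runs per scenario, with overdispersed AECOPD counts (mean 1, 80% sampled). The ordinary large-sample standard error (Fleiss–Cohen–Everitt) averaged 0.0348, so the ordinary half-width is 1.96 × 0.0348 = 0.068. True half-width is 1.96 × the empirical SD. ICC is the assumed latent intraclass correlation within patient.

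| ICC carriage | ICC culture given PCR | Empirical SD | True half-width | Variance design effect | Coverage, ordinary CI | Coverage, patient-clustered CI |
|---|---|---|---|---|---|---|
| 0 | 0 | 0.0345 | 0.068 | 0.98 | 94.8% | 94.5% |
| 0.5 | 0 | 0.0353 | 0.069 | 1.03 | 94.9% | 95.0% |
| 0 | 0.3 | 0.0374 | 0.073 | 1.15 | 93.1% | 94.1% |
| 0.5 | 0.3 | 0.0390 | 0.076 | 1.26 | 92.2% | 94.9% |
| 0.5 | 0.6 | 0.0427 | 0.084 | 1.50 | 89.1% | 95.0% |
| 0.8 | 0.6 | 0.0473 | 0.093 | 1.85 | 84.7% | 93.9% |
| 0.8 | 0.8 | 0.0517 | 0.101 | 2.21 | 81.4% | 94.4% |

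From 0.5/0.3 to 0.8/0.8, the correct interval is 0.076 / 0.068 = 1.12 to 0.101 / 0.068 = 1.49 times the ordinary width. The second row shows that correlated carriage on its own does essentially no harm.

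**5. Variations.**
- AECOPD samples alone (about 144): over the same ICC range, ordinary coverage is 92.1% to 86.7%, with half-width 0.152 to 0.182 against 0.143. The clustered interval covers 92% to 93.5% here, so it helps but does not fully restore 95%.
- PCR prevalence 10% (kappa 0.531, all visits): ordinary coverage is 92.3% at ICCs 0.5/0.3 and 85.5% at 0.8/0.6.

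**6. What it means for the bands.** Take an estimate of 0.50 and carry the half-widths over as an approximation. The ordinary interval, 0.50 ± 0.068, is 0.43 to 0.57 and lies inside the moderate band. With ± 0.101 it is 0.40 to 0.60 and reaches both edges.

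**The case against.** **The method is not stated, so it is not stated wrongly.** A reader might infer that the SAP prescribes an independence-based formula. It does not: it gives no formula, standard error or code for kappa, and the mock tables, which might carry one, are a separate document. What stands is that the method is unspecified and that the usual default ignores repeated samples.

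**Correlated positivity is not correlated disagreement.** A reader might also infer that, because the SAP models correlation in positivity, the kappa interval must be too narrow. The check does not support that step: carriage ICC 0.5 with no correlation in culture given PCR leaves coverage at 94.9%. The shortfall needs culture yield, given PCR, to be correlated within patient, and no section gives evidence of its size. This objection stands and makes the conclusion conditional.

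**The tables may be kept apart by visit type.** The wording of SAP 6.3.1 can be read as one pooled table or as one for stable and one for AECOPD visits; the GEE code in 6.2.1 does separate them. Pooling is the more literal reading. Separate tables would still leave up to three stable samples per patient, so the problem would shrink rather than disappear.

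**Laboratory effects are not patient effects.** Disagreement shared by a laboratory is shared across its patients, and a patient-level correction does not capture all of that. This also stands.

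**Materiality.** The bands apply to kappa itself and no rule uses its interval. SAP section 7 calls all analyses descriptive. At moderate correlations the half-width changes by about 0.01 to 0.02. This is fair, and it limits the weight of the point.

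**Conclusion.** The point holds in conditional form. SAP 6.3.1 attaches a 95% CI to a kappa built from about 3.5 samples per patient and leaves open how repeated samples are handled. The default interval will be too narrow if culture–PCR disagreement is correlated within patient. That is plausible, but it is neither shown nor quantified in the documents.

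The coverage range of about 92% to 81%, and the widening of 12% to 49%, rest on the assumed ICCs, the 90% stable sampling rate and the assumed prevalence and culture yield. The upper end needs ICCs of 0.8 for both carriage and culture given PCR; near-zero correlation in disagreement would leave the interval essentially correct. The kappa estimate is not biased by this. Importance is minor to moderate: it concerns the precision of a descriptive secondary objective.

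**What to change.** Add a sentence to SAP 6.3.1: the kappa point estimate is unchanged, and its 95% CI comes from a bootstrap that resamples patients with all their samples, or from a patient-clustered variance. Fix the number of replicates and the seed in advance. Report kappa for stable and AECOPD samples separately as well as pooled, which also settles how the visit wording is to be read.

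Resampling may be stratified by site if wanted. Either way, the SAP should say that a patient-level method corrects for repeated samples but not for all between-laboratory variation in culture.

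The cost is a short program on data already collected. The downside is wider intervals if the correlation is real, and visibly less precision in the AECOPD-only table, where the ordinary half-width is already about 0.143.
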